## **5. Baseline comparisons of key characteristics**

The following baseline characteristics of patients on each of the five study arms (including the non-randomised MDR group) will be tabulated and compared for each analysis population: age, gender, race, region, site, smoking status, HIV status/CD4 count, cavitation (based on blinded, central assessment of the chest radiograph (refer to Central Chest X-ray Manual), initial bacterial load in sputum as indicated by baseline Time to Positivity (TTP) result from MGIT, resistance to first and second line antibiotics and whether or not the patient is taking efavirenz.

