## **7. Determination of statistical non-inferiority**

The first comparison to be tested will be the MPa200Z 6 month experimental regimen against the standard regimen. The second comparison to be tested will be the MPa200Z 4 month experimental regimen against the standard regimen. The third comparison to be tested will be the MPa100Z 4 month experimental regimen against the standard regimen. To preserve the type I error rate, the second comparison will only be tested if non-inferiority is demonstrated with the 6 month experimental regimen. Similarly the third hypothesis will only be tested if non-inferiority of the PA-824 200mg 4 month regimen has been demonstrated. This strategy means no adjustments are required for multiple comparisons.

Non-inferiority will be assessed using the upper bound of the two-sided 95% confidence interval for the difference between the proportion of participants who are classified as having an unfavourable status on the intervention and the control regimen.

If the upper bound of the two-sided 95% confidence limit for the difference, proportion with unfavourable status on intervention arm less the proportion with unfavourable outcome on the control arm, is less than 12% (the margin of non-inferiority) the intervention will be considered to be non-inferior to the control arm on that comparison.

The PP and MITT analyses will be considered primary. However, in order to declare an intervention to be non-inferior, consistent results should be obtained from the ITT analysis and from sensitivity and subgroup analyses, although not all of these will necessarily satisfy the strict definition of non-inferiority.

All primary efficacy analyses of the three main analysis populations will be adjusted for HIV status and cavitation, using a stratified analysis of the risk difference from each stratum using Cochran-Mantel-Haenszel weights.

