### **9.2. Additional covariate adjustment**

Additional baseline covariates listed in section 6 will be considered for a secondary adjusted analysis for the primary endpoint. This will be a secondary analysis, assuming baseline covariates are well balanced across the treatment arms.

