### **10.3 Time to sputum culture conversion to negative status**

Time to culture negative status (first of two negative cultures without an intervening positive culture) will be analysed using survival analysis techniques, Kaplan Meier plots and Cox proportional hazard regression.

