### **10.4. Culture conversion status at 4, 8, 12 and 17 weeks**

Patients will be classified as being culture positive, culture negative, dead or unassessable at 4, 8, 12 and 17 weeks. Every effort will be made to obtain a sputum sample from all patients but it is recognised that some patients may not have produced any sputum in the preceding week and may be unable to do so when requested. Patients who cannot produce sputum will be classified as being culture negative at that time point. The proportion culture negative will be those classified as being culture negative divided by the total considered culture negative, culture positive or have died.

In a separate sensitivity analysis patients who are unassessable at this time point for whatever reason (e.g. culture contaminated) will be considered to be culture positive unless they are culture negative on at least two previous assessments in which case they will be considered to be culture negative. This does not include patients who could not produce sputum at 4, 8, 12 and 17 weeks, who are considered to be culture negative.

Differences from the control regimen in culture negativity at weeks 4, 8, 12 and 17 will be expressed as a difference in proportions with corresponding 2-sided 95% confidence intervals.

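### Sections 10.3 and 10.4 name no baseline adjustment for the culture-conversion comparisons, although HIV status, cavitation and baseline TTP are all recorded; prespecifying it would gain some precision at little cost

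*SAP*

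**What the plan says.** - **Section 10.4** (status at weeks 4, 8, 12 and 17): "Differences from the control regimen in culture negativity at weeks 4, 8, 12 and 17 will be expressed as a difference in proportions". Each estimate comes with an interval at the 95% level, two-sided. No strata, covariates, test, margin or power are given.
- **Section 10.3** (time to culture negative status): "will be analysed using survival analysis techniques, Kaplan Meier plots and Cox proportional hazard regression". Again no strata or covariates.
- **Section 7**: "All primary efficacy analyses of the three main analysis populations will be adjusted for HIV status and cavitation", by a risk difference with Cochran-Mantel-Haenszel (CMH) weights. The wording covers the primary analyses only.
- **Section 9.2**: further baseline covariates "will be considered for a secondary adjusted analysis for the primary endpoint", so this adjustment too stops at the primary endpoint.
- **Section 10.1** expressly repeats the 12-month methods for the 24-month endpoint. Sections 10.3 and 10.4 have no such clause.
- **Section 5** lists "initial bacterial load in sputum as indicated by baseline Time to Positivity (TTP) result from MGIT" among the baseline characteristics. Section 11 uses it, HIV status and cavitation as subgroup factors. All three covariates are therefore available.

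**The concern.** How soon a patient's cultures turn negative is likely to depend on the starting bacterial load, and baseline TTP is the SAP's own measure of that load. If the comparison with control ignores it, between-patient variation that could be removed stays in the standard error. The 10.4 intervals are then wider than necessary, and the Cox comparison in 10.3 has less power to detect a difference in speed of conversion.

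There is also a prespecification point. If adjustment is left open, the covariates for these endpoints could be chosen after data are seen, in an open-label trial. One sentence settles both matters.

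**Working it through.** **1. The plan's own figure.** The SAP gives no sample size or power for culture conversion. Its only figure is 255 per arm for the 12-month primary endpoint (Appendix 1), and it reproduces:

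- 2 × 0.16 × 0.84 × (1.960 + 1.282)² / 0.12² = 196.1 evaluable per arm
- 196.1 / (1 − 0.15 − 0.08) = 254.7, i.e. 255

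This figure does not bear on culture conversion. It does give a working number: 300 × 0.77 = 231 evaluable per arm. That the same share is evaluable at weeks 4-17 is an assumption.

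**2. Variance removed by stratifying the 10.4 difference.** To a good approximation, stratification multiplies the variance of the risk difference by 1 − R². Here R² is the between-stratum variance of the negativity proportion divided by p(1 − p).

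Assumptions, none from the SAP: 60% with cavitation, 20% HIV positive, half with high load by TTP, independent factors, and the odds ratios for being culture negative shown in the table.

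Example, 70% negative overall and cavitation odds ratio 0.5 only: the stratum proportions are about 0.784 (no cavity) and 0.644 (cavity). R² = 0.4 × 0.6 × (0.784 − 0.644)² / (0.7 × 0.3) = 0.0047 / 0.21 = 0.022.

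| Negative overall | Cav 0.5 | Cav 0.5, HIV 1.5 | Cav 0.33, HIV 1.5 | Cav 0.5, HIV 1.5, TTP 0.33 | Cav 0.33, HIV 1.5, TTP 0.2 |
|---|---|---|---|---|---|
| 50% | 0.028 | 0.034 | 0.075 | 0.098 | 0.184 |
| 70% | 0.022 | 0.027 | 0.057 | 0.082 | 0.158 |
| 90% | 0.009 | 0.011 | 0.022 | 0.036 | 0.070 |

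HIV status and cavitation alone remove about 1-8% of the variance. Adding TTP makes it about 4-18%. At 90% negative the ranges are about 1-2% and 4-7%.

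**3. A direct check with four strata.** Assume four equal, evenly spaced strata, 250 per arm, and a 10-point effect added to every stratum.

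- Control negativity 45-85%: between-stratum variance 0.0222 per arm; total variances 0.2275 and 0.1875. Variance ratio = 1 − 0.0444 / 0.415 = 0.89. Power 69% unadjusted, 74% stratified.
- Control negativity 35-90%: between-stratum variance 0.0420; total variances 0.2344 and 0.1994. Variance ratio = 1 − 0.0840 / 0.4338 = 0.81. Power 67% unadjusted, 76% stratified.

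Simulations of 4,000 trials with these spreads gave ratios of 0.90 and 0.80-0.83, which takes the upper end to about 20%. The variance ratios are the stable result; absolute power moves with the assumed stratum sizes. The wider spread also puts the top experimental stratum at 100%, so it is an extreme case.

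**4. What that means for precision.** No power target exists, so take 80% unadjusted power as a reference. Adjusted power = Φ(2.802 / √(1 − R²) − 1.960). The half-width column assumes 70% negative on control, and equivalent N is 231 / (1 − R²).

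| R² | Power | 95% CI half-width (points) | Equivalent N per arm |
|---|---|---|---|
| 0 | 80.0% | 7.8 | 231 |
| 0.02 | 80.8% | 7.7 | 236 |
| 0.05 | 82.0% | 7.6 | 243 |
| 0.10 | 84.0% | 7.4 | 257 |
| 0.15 | 86.0% | 7.2 | 272 |
| 0.20 | 87.9% | 7.0 | 289 |

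Over the ranges in step 2 this is roughly 0.4 to 3 power points for HIV status and cavitation, and 1.5 to 7 with TTP.

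**5. The Cox analysis in 10.3.** Assume 250 per arm, conditional hazard ratio 1.3, Weibull conversion times, interval visits to week 17 and Efron ties. Two independent sets of 400 simulated trials per setting gave:

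| Log-HR per SD of load | Unadjusted HR | Unadjusted power | Adjusted HR | Adjusted power |
|---|---|---|---|---|
| 0.3 | 1.27-1.28 | 76-78% | 1.29-1.30 | 81-84% |
| 0.5 | 1.24-1.25 | 68-69% | about 1.30 | 81-84% |
| 0.7 | 1.21-1.22 | 55-59% | 1.29-1.30 | 78-81% |

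Monte Carlo error is about √(0.75 × 0.25 / 400) = 2.2 points. Within each set the gain is 5-6, 12-16 and 22-23 points. It depends almost entirely on the assumed strength of load.

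**The case against.** The other side has a good case, and most of it stands.

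- **Silence is not a statement.** A reader might infer that the SAP commits to unadjusted analysis. It does not say so. A CMH-weighted risk difference is also a difference in proportions, a Cox model can carry covariates, and section 9.1 uses the word unadjusted where it is meant. Against that, sections 7 and 9.2 confine adjustment to the primary endpoint, and section 10.1 carries methods over explicitly where 10.3 and 10.4 do not. No adjustment is the natural reading; the firm finding is that none is specified.
- **No power target is missed.** These are secondary estimates with no stated test, margin or power. The right word is precision.
- **The unadjusted result is not biased.** A reader might infer that chance imbalance in load would pass as a regimen effect. Randomisation makes the unadjusted difference valid, its interval already allows for chance imbalance, and section 5 tabulates baseline TTP by arm.
- **The hazard ratio nearer 1 is not an error.** It reflects non-collapsibility: marginal and conditional hazard ratios are different quantities.
- **Load has its own analysis.** Section 10.2 models TTP decline in a separate document. That does not fix the covariates for 10.3 and 10.4.

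What survives is narrow: adjustment for baseline values already in hand would gain precision, and the plan does not specify it.

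**Conclusion.** The point holds as an optional improvement. Sections 10.3 and 10.4 name no adjustment, although section 7 already sets out a stratified method and section 5 records the covariate most likely to matter. As written, the comparisons are valid but less precise than they need be.

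For 10.4 the variance reduction is about 1-8% from HIV status and cavitation and about 4-20% with baseline TTP. Late visits may see little of it: with assumed strata of 80-97% or 88-97% negative, the reduction is only about 4% or 2%. For 10.3 the simulated power gain ran from 5 to 23 points over the assumed strengths of load. Every one of these figures rests on assumed prognostic strengths.

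A reader might extend the point to the Cox model in section 9.3. That concerns a different endpoint, and no calculation here supports the extension. Non-inferiority is decided on the 12-month endpoint, for which adjustment is already specified, so the trial's main conclusion does not change.

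**What to change.** - **Section 10.4:** report the section 7 CMH-weighted risk difference, stratified by HIV status and cavitation, with baseline TTP as a further stratum (above or below the pooled median, missing as its own category). This gives up to 2 × 2 × 3 = 12 strata, so prespecify how sparse ones are collapsed. For example, when a stratum is empty in one arm of a comparison, collapse over HIV status first; it has the weakest assumed effect above.
- **Section 10.3:** stratify the Cox model by HIV status and cavitation, with baseline TTP as a covariate and an indicator for missing values. State that the hazard ratio is conditional on these covariates.
- **Missing TTP:** section 4.1 keeps patients whose baseline culture is contaminated or negative if another sample, up to week 4, confirms the disease, so the missing category may be populated. TTP from a sample taken after treatment starts should not stand in for baseline.
- **Both sections:** keep the unadjusted results as supportive, as section 9.1 does for the primary endpoint.

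The cost is SAP wording and minor programming, a missing-TTP category, and a conditional hazard ratio that readers must not compare directly with the unadjusted one. No new data, visits or patients are needed.

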### **10.5. TB symptoms**

Analyses of symptoms will include time to resolution of symptoms. This will be defined as the first of two consecutive attendances when the patient is free from TB related symptoms.

Please refer to Safety SAP for other analyses of TB symptoms.

### **10.6. Patient reported health status**

Please refer to Safety SAP.

## **11. Sub-group analyses**

To assess consistency of outcome, the following sub-group analyses (with tests for interaction) of the primary endpoint on the per-protocol and MITT analysis populations will be performed according to: age; gender; race; region; smoking status; HIV status/CD4 count; cavitation (based on blinded, central assessment of the chest radiograph), initial bacterial load in sputum as indicated by baseline TTP result from MGIT; whether the patient is taking efavirenz or not during the treatment period.

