## 1. Introduction

This document outlines the efficacy statistical analysis plan (SAP) for the protocol STAND, a phase 3 trial of three experimental regimens of the combination regimen of moxifloxacin, PA-824 and pyrazinamide (MPaZ).

The primary efficacy analysis will be conducted using culture results from liquid culture (MGIT) and will evaluate the hypothesis that in the patients with drug-sensitive tuberculosis (DS-TB) treated with any of the experimental MPaZ regimens, the incidence of bacteriologic failure or relapse or clinical failure at 12 months from the start of therapy is non-inferior to the proportion observed in patients who are treated with the 6 month standard isoniazid, rifampicin, pyrazinamide, ethambutol (HRZE/HR) regimen.

The three experimental regimens detailed below will be compared to the control regimen in the order specified. For the second and third comparison, statistical inference will only be made if non-inferiority is declared on the preceding comparison:

*First comparison:* MPaZ with 200mg PA-824 (MPa200Z) for 6 months vs HRZE/HR

*Second comparison:* MPaZ with 200mg PA-824 (MPa200Z) for 4 months vs HRZE/HR

*Third comparison:* MPaZ with 100mg PA-824 (MPa100Z) for 4 months vs HRZE/HR

300 patients per randomised arm will be recruited. See Appendix 1 for details of the sample size. An additional non-randomised group of up to 300 patients with multi-drug resistant (MDR) TB will be treated with regimen MPa200Z for 6 months. No formal statistical analysis is planned for this group and unless otherwise stated all analyses outlined in this document refer to the analysis of the 4 randomised groups of the DS-TB patients.

While STAND is an open label study, only members of the Data Safety Monitoring Committee (DSMC) and the unblinded statistician(s) will have access to data **grouped by study arm**. Access to data by investigators, CRO and TB Alliance staff will not allow any access to data grouped by study arm. In addition, site staff will be strongly discouraged from attempting to aggregate by treatment arm at a site level.

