**Relapse or Bacteriologic relapse** is defined as failing to maintain culture negative status or being declared an unfavourable outcome after the end of treatment (either 4 or 6 months) in those patients who attained culture negative status by the end of treatment, and were re-infected with the **same** (as per the STAND Laboratory Manual) *Mycobacterium tuberculosis (MTB)* strain.

**Reinfection or Bacteriologic Reinfection** is defined as failing to maintain culture negative status or being declared an unfavourable outcome after the end of treatment (either 4 or 6 months) in those patients who attained culture negative status by the end of treatment and were infected with a *Mycobacterium tuberculosis (MTB)* strain that is **different** (as per the STAND Laboratory Manual) from the infecting strain at baseline.

**Clinical failure** is defined as a change from protocol-specified TB treatment or retreatment for TB during follow up as determined by the treating physician, or TB-related death.

The **treatment period** is defined as either 4 or 6 months from start of therapy depending on allocated treatment regimen and the **follow-up period** is defined as the period after the end of treatment to the end of follow-up.

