### 3.4. Timing of events

In all analyses, visit date rather than day or week number will be used to define the timing of events. The 4 month regimens will be taken as 17 weeks (119 days) and the 6 month regimens as 26 weeks (182 days) from the start of therapy. For the end of treatment visit (months 4/6), a  $\pm 1$  week window will be applied (as per the protocol). For the 12 and 24 month visits, a window of  $\pm 2$  weeks will be applied (as per the protocol).

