#### **4.3. Additional exclusions from PP analysis**

1. Patients lost to follow-up or withdrawn before the end of treatment, unless they have already been classified as having an unfavourable outcome.

2. Patients whose treatment was modified or extended for reasons (e.g. an adverse drug reaction or pregnancy) other than an unfavourable therapeutic response to treatment, unless they have already been classified as having an unfavourable outcome.

3. Patients not meeting the definition of having received an adequate amount of their allocated study regimen (see section 4.5 for definition), provided they have not already been classified as having an unfavourable outcome.

4. Patients who are classified as “major protocol deviations” (see below), unless they have already been classified as having an unfavourable outcome on the basis of data obtained prior to the protocol deviation.

A list of all protocol deviations will be compiled throughout the course of the study.

A **Major Protocol Deviation** is defined as a serious protocol deviation which is likely to affect to a significant degree the safety or physical or mental integrity of the subjects of the trial or the scientific value of the trial. These patients will be included in the ITT and MITT analyses, but not in the Per Protocol analysis. A list of all major protocol deviations will be approved by the study Coordinating Investigator before database lock.

A **Minor Protocol Deviation** is defined as a technical deviation which does not result in harm to the trial subjects or significantly affect the scientific value of the reported results of the trial.

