### **6.1.3. Unfavourable status in MITT population**

1. Patients not classified as having achieved or maintained culture negative status when last seen, or
2. Patients previously classified as having culture negative status who, following the end of treatment, have two positive cultures without an intervening negative culture, (however, see Section 3.3 for an exception), or
3. Patients who had a positive culture not followed by at least two negative cultures when last seen, or
4. Patients dying from any cause during treatment, except from violent or accidental cause (e.g. road traffic accident), not including suicide (eg, suicide will be considered an unfavourable outcome) or
5. Patients definitely or possibly dying from TB related cause during the follow-up phase or
6. Patients requiring an extension of their treatment beyond that permitted by the protocol, a restart or a change of treatment for any reason except reinfection or pregnancy, or
7. Patients failing to complete an adequate course of treatment, as defined in section 4.5, who were unassessable at 12 months, or
8. Patients lost to follow up or withdrawn from the study before the end of treatment

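### Section 11 defines the efavirenz subgroup by use during treatment, a post-randomisation status read over unequal windows in two of the three comparisons, although baseline use is already listed in Section 5

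*SAP*

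**What the plan says.** SAP Section 11 plans subgroup analyses of the primary endpoint, with interaction tests, in the MITT and PP populations. The last of nine factors is "whether the patient is taking efavirenz or not during the treatment period". The other eight (age, gender, race, region, smoking, HIV status/CD4 count, cavitation, baseline time to positivity) can all be fixed at baseline.

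Section 3.1 has the treatment period "defined as either 4 or 6 months from start of therapy depending on allocated treatment regimen". Section 3.4 puts this at 119 days for 4-month regimens and 182 days for 6-month regimens. Under Section 1, the second and third comparisons set a 4-month arm against patients "treated with the 6 month standard isoniazid, rifampicin, pyrazinamide, ethambutol (HRZE/HR) regimen".

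Section 5 already includes "whether or not the patient is taking efavirenz" in its list of baseline characteristics.

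On the role of the subgroups, Section 7 says that "consistent results should be obtained from the ITT analysis and from sensitivity and subgroup analyses, although not all of these will necessarily satisfy" the formal definition of non-inferiority.

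**The concern.** A subgroup contrast is a randomised comparison only if membership is settled before treatment can influence it. Here it is not, for two reasons.

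- **Outcome affects membership.** A patient who dies or leaves early has less time to start efavirenz, so later starters are selected for having had no early event. In MITT these events are themselves unfavourable: most on-treatment deaths count under Section 6.1.3 item 4, and item 8 adds "Patients lost to follow up or withdrawn from the study before the end of treatment". The problem is smaller in PP, because Section 4.3 excludes "Patients lost to follow-up or withdrawn before the end of treatment, unless they have already been classified as having an unfavourable outcome". On-treatment deaths still count there under Section 6.1.4 item 4.
- **Arm affects membership.** In the second and third comparisons, control patients have 63 more days (182 - 119) in which to be labelled users. The first comparison has equal windows.

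The trial is also open label, so starting efavirenz could itself depend on the arm. At stake is whether an apparent efavirenz interaction, or its absence, partly reflects labelling. The primary non-inferiority test does not use this variable.

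**Working it through.** The SAP gives no figure for efavirenz use, so there is none to reproduce. The check asks how large a false interaction the definition can create when efavirenz has no effect and both arms have the same unfavourable rate.

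**Inputs from the SAP:** windows of 119 and 182 days (Section 3.4); 16% unfavourable, 15% unassessable, 8% excluded for isoniazid mono-resistance, 300 per arm (Appendix 1).

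**Assumed:** share b on efavirenz at baseline, 2, 5 or 10%; share s of the rest who would start, 5, 10 or 15%, with starts uniform over days 14-182; share f of unfavourable outcomes that fall on treatment, 30, 45 or 60%. A user is a patient on efavirenz at baseline, or one who starts before both the unfavourable event and the end of the window.

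**Formulas.** Let w be the probability that a start falls inside the window, and v the probability that it does so and also precedes a uniformly timed on-treatment event.

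- Users: U = b + (1 - b)s[w(1 - 0.16f) + v(0.16f)]
- Unfavourable users: Y = 0.16b + (1 - b)s[w(0.16)(1 - f) + v(0.16f)]
- Rate in users: Y/U. Rate in non-users: (0.16 - Y)/(1 - U)
- Interaction: (4-month minus control in users) minus (the same in non-users)

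**Mid-case** (b = 5%, s = 10%, f = 45%, on-treatment events uniform over 182 days in both arms). Here 0.16f = 0.072 and 0.16(1 - f) = 0.088.

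*Control, 182 days.* w = 1. The mean start day is 98, so v = (182 - 98)/182 = 0.4615.
- U = 0.05 + 0.095(0.928 + 0.4615 x 0.072) = 0.1413, or 42 of 300
- Y = 0.008 + 0.095(0.088 + 0.4615 x 0.072) = 0.01952
- Users 13.8%, non-users 16.4%

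*4-month arm, 119 days.* w = 105/168 = 0.625. The mean start day within the window is 66.5, so v = 0.625(182 - 66.5)/182 = 0.3966.
- U = 0.05 + 0.095(0.625 x 0.928 + 0.3966 x 0.072) = 0.1078, or 32 of 300
- Y = 0.008 + 0.095(0.625 x 0.088 + 0.3966 x 0.072) = 0.01594
- Users 14.8%, non-users 16.1%

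Interaction = (14.78 - 13.81) - (16.15 - 16.36) = +1.2 points, although nothing differs between the arms except the window.

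**Whole grid, second and third comparisons** (percentage points). For raised starter risk, the overall rate among baseline non-users is held at 16%.

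| Starts | On-treatment events uniform over | Starters at average risk | Starters at 1.5-2 times the risk of others |
|---|---|---|---|
| Days 14-182 | 182 days in both arms | +0.42 to +1.97 | -0.96 to +1.83 |
| Days 14-182 | each arm's own period | +0.20 to +0.75 | -1.64 to -0.18 |
| Days 14-84 | 182 days in both arms | 0.00 | |
| Days 14-84 | each arm's own period | -1.27 to -0.21 | |

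**First comparison** (182 v 182 days): 0.00 throughout when unfavourable outcomes are timed alike in both arms. It reaches 2.4 points either way only if the on-treatment share is 30% in one arm and 60% in the other.

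**Higher starting rates.** Among baseline non-users alone, if 20-60% started at a constant rate and 8 or 12 of the 16 points fell within 182 days, simulation gave false interactions of about 1.5 to 5.1 points. Across the whole trial the figure would be smaller.

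**Precision.** Assessable patients per arm: 300(1 - 0.15 - 0.08) = 231. With 10% users, that is 23.1 users and 207.9 non-users. Standard error = sqrt[2(0.16)(0.84)/23.1 + 2(0.16)(0.84)/207.9] = 11.4 points.

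**The case against.** The strongest reply is that it hardly matters. A 2.0-point artefact is under 0.2 standard errors (2.0/11.4) and would move the rejection rate of a two-sided 5% interaction test only to about 5.35%; the mid-case moves it to 5.13%. Every efavirenz input is assumed, and the sign changes with the timing of starts and the risk of starters. If few patients start or stop after randomisation, the bias is negligible. Efavirenz is one of nine factors, no decision rule uses its p-value, and Section 7 does not require every supportive analysis to meet the margin. All of this stands, and it limits the weight of the point.

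The second reply is that the wording may be deliberate. If the question is co-administration with study drug, a 4-month patient who starts on day 150 had none and is correctly labelled a non-user. That is a fair reading of the aim. But a label can describe exposure accurately and still fail to define comparable groups, and in control the same day-150 start makes a user.

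The third reply is that the phrase need not mean ever on efavirenz during the period. That is so: the SAP has no rule for patients who start or stop, and the calculation had to supply one. Any rule based on use after randomisation would still leave membership open to post-randomisation events.

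**Conclusion.** The concern holds. Section 11, read with Sections 3.1 and 3.4, makes membership of the efavirenz subgroup depend on what happens after randomisation in all three comparisons, and on allocated arm in the second and third. Under the assumed rates of 2-10% baseline use and 5-15% later starting, the false interaction in those two comparisons stays within about 2 points in either direction. Noise of about 11 points would hide it in a single trial, but a larger sample would not remove it. It is zero in the first comparison if outcomes are timed alike in the two arms. The primary test, the type I error rate and the sample size are unaffected. The change is still worth making, because subgroup consistency feeds the Section 7 judgement and the SAP already lists a variable free of the problem.

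**What to change.** In Section 11, define the subgroup by efavirenz use at baseline, as listed in Section 5, for all arms. Tabulate on-treatment efavirenz exposure by arm as description only, outside the consistency assessment. Under the same no-effect assumptions the false interaction is then zero by construction, because the length of the window no longer plays a part.

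The text change is one phrase, and no other analysis is affected. The statistical cost is some dilution of a true co-administration effect, since later starters count as non-users. If a share s of baseline non-users start, about 1 - s of the contrast is kept: 85-95% for s of 5-15%, and less if baseline users stop.
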